**Appendix 3. Schedule of Assessments for Pharmacokinetics, Pharmacodynamics, and Biomarkers\***

Timepoints a			Ibrutinib PK	Ibrutinib Biomarker/ Pharmacodynamics c	MEDI4736 PK	MEDI4736 Pharmacodynamics
Screening				X		
Cycle 1	Day 1	Predose b	X	X	X	X (includes ADA)
		1 hr postdose ibrutinib ( $\pm$ 15 min)	X		X d	X d
		2 hr postdose ibrutinib ( $\pm$ 15 min)	X			
		4 hr postdose ibrutinib ( $\pm$ 30 min)	X	X		
	Day 2	24 hr postdose Day 1 ( $\pm$ 2 h)	X	X		
	Day 15	Predose b		X	X	X
		4 hr postdose ibrutinib ( $\pm$ 30 min)		X		
Cycle 2	Day 1	Predose b		X		
	Day 15	Predose b		X		
Cycle 3	Day 1	Predose b	X	X	X	X (includes ADA)
		1 hr postdose ibrutinib ( $\pm$ 15 min)	X		X d	X d
		2 hr postdose ibrutinib ( $\pm$ 15 min)	X			
		4 hr postdose ibrutinib ( $\pm$ 30 min)	X			
	Day 15	Predose b		X		
Cycle 4	Day 1	Predose b		X		
Cycle 5	Day 1	Predose b		X		
Cycle 6	Day 1	Predose b		X	X	X (includes ADA)
		1 hr postdose ibrutinib ( $\pm$ 15 min)			X d	X d
Cycles 9, 12, 15	Day 1	Predose b		X	X	X (includes ADA)
Cycle 18 & q3 cycles thereafter	Day 1	Predose b		X		
At CR and/or Progressive Disease e				X		
Treatment Termination Visit (Optional)				X		
End-of-Treatment Visit for ibrutinib (30 Day Follow-up) e				X		
90 Day Follow-up Visit for MEDI4736 e					X	X

**Abbreviations:** ADA = anti-drug antibodies; CR = complete response; PK = pharmacokinetics

\* Please refer to the PPD Laboratory Flowchart for a complete list of lab samples to be collected at each time point

- a. MEDI4736 will be administered as an IV infusion approximately 1 hour in duration. Subjects are expected to take ibrutinib PO within 15 minutes AFTER the end of the MEDI4736 infusion.
- b. Predose=predose MEDI4736 infusion and ibrutinib PO
- c. This column combines both ibrutinib biomarker and pharmacodynamics (ibrutinib PD CPT) collections. Please refer to the collection flow chart for exact timepoints of each collection.
- d. 1-hr post dose ibrutinib is approximately 1 hr (+ up to 15 min) after the end of the MEDI4736 infusion and approximately 2 hr (+ up to 15 min) after the initiation of MEDI4736 infusion. Samples are to be drawn at the same time.
- e. If the visit occurs at a routine study visit where the samples are already being drawn, a separate set of samples is not required.

**Appendix 4. ECOG Performance Status Scores**

Status	Eastern Cooperative Oncology Group (ECOG) Performance Status**
0	Fully active, able to carry on all predisease performance without restriction.
1	Restricted in physically strenuous activity but ambulatory and able to carry out work of a light or sedentary nature, eg, light housework, office work.
2	Ambulatory and capable of all self-care, but unable to carry out any work activities. Up and about more than 50% of waking hours.
3	Capable of only limited self-care, confined to bed or chair more than 50% of waking hours.
4	Completely disabled. Cannot carry on any self-care. Totally confined to bed or chair.
5	Dead.

Available at: [http://www.ecog.org/general/perf\\_stat.html](http://www.ecog.org/general/perf_stat.html). Accessed January 4, 2008.

## Appendix 5. Inhibitors and Inducers of CYP3A

Inhibitors and inducers of CYP3A enzymes are defined as follows. Refer to [Section 6.2.1](#) on instructions for concomitant use of CYP3A inhibitors and inducers with ibrutinib. Further information can be found at the following website: <http://medicine.iupui.edu/clinpharm/ddis/main-table/>.

Inhibitors of CYP3A	Inducers of CYP3A
Strong inhibitors:	
indinavir	carbamazepine
nefnavir	efavirenz
ritonavir	nevirapine
clarithromycin	barbiturates
itraconazole	glucocorticoids
ketoconazole	modafinil
nefazodone	oxcarbazepine
saquinavir	phenobarbital
suboxone	phenytoin
telithromycin	pioglitazone
cobicistat	rifabutin
boceprevir	rifampin
mibefradil	St. John's Wort
telaprevir	troglitazone
troleandomycin	
posaconazole	
Moderate inhibitors:	
aprepitant	
amprenavir	
amiodarone	
atazanavir	
ciprofloxacin	
crizotinib	
darunavir/ritonavir	
dronedarone	
erythromycin	
diltiazem	
fluconazole	
fosamprenavir	
grapefruit juice	
Seville orange juice	
verapamil	
voriconazole	
imatinib	
Weak inhibitors:	
cimetidine	
fluvoxamine	
All other inhibitors:	
chloramphenicol	
delavirdine	
diethyl-dithiocarbamate	
gestodene	
mifepristone	
norfloxacin	
norfluoxetine	
star fruit	

**Appendix 6. New York Heart Association (NYHA) Functional Classification**

Class	Functional Capacity: How a patient with cardiac disease feels during physical activity
I	Patients with cardiac disease but resulting in no limitation of physical activity. Ordinary physical activity does not cause undue fatigue, palpitation, dyspnea or anginal pain.
II	Patients with cardiac disease resulting in slight limitation of physical activity. They are comfortable at rest. Ordinary physical activity results in fatigue, palpitation, dyspnea or anginal pain.
III	Patients with cardiac disease resulting in marked limitation of physical activity. They are comfortable at rest. Less than ordinary activity causes fatigue, palpitation, dyspnea or anginal pain.
IV	Patients with cardiac disease resulting in inability to carry on any physical activity without discomfort. Symptoms of heart failure or the anginal syndrome may be present even at rest. If any physical activity is undertaken, discomfort increases.

From: [http://www.heart.org/HEARTORG/Conditions/HeartFailure/AboutHeartFailure/Classes-of-Heart-Failure\\_UCM\\_306328\\_Article.jsp](http://www.heart.org/HEARTORG/Conditions/HeartFailure/AboutHeartFailure/Classes-of-Heart-Failure_UCM_306328_Article.jsp)

The Criteria Committee of the New York Heart Association. Nomenclature and Criteria for Diagnosis of Diseases of the Heart and Great Vessels. 9th ed. Boston, Mass: Little, Brown & Co; 1994:253-256.

## Appendix 7. Hepatitis Serology Chart

Hepatitis B serologic testing involves measurement of several hepatitis B virus (HBV)-specific antigens and antibodies. Different serologic “markers” or combinations of markers are used to identify different phases of HBV infection and to determine whether a patient has acute or chronic HBV infection, is immune to HBV as a result of prior infection or vaccination, or is susceptible to infection.

Interpretation of Hepatitis B Serologic Test Results		
HBsAg	negative	
anti-HBc	negative	Susceptible
anti-HBs	negative	
HBsAg	negative	
anti-HBc	positive	Immune due to natural infection
anti-HBs	positive	
HBsAg	negative	
anti-HBc	negative	Immune due to hepatitis B vaccination
anti-HBs	positive	
HBsAg	positive	
anti-HBc	positive	
IgM anti-HBc	positive	Acutely infected
anti-HBs	negative	
HBsAg	positive	
anti-HBc	positive	
IgM anti-HBc	negative	Chronically infected
anti-HBs	negative	
HBsAg	negative	Interpretation unclear; four possibilities:
		1. Resolved infection (most common)
anti-HBc	positive	2. False-positive anti-HBc, thus susceptible
		3. “Low level” chronic infection
anti-HBs	negative	4. Resolving acute infection
		4. Resolving acute infection

- **Hepatitis B surface antigen (HBsAg):** A protein on the surface of hepatitis B virus; it can be detected in high levels in serum during acute or chronic hepatitis B virus infection. The presence of HBsAg indicates that the person is infectious. The body normally produces antibodies to HBsAg as part of the normal immune response to infection. HBsAg is the antigen used to make hepatitis B vaccine.
- **Hepatitis B surface antibody (anti-HBs):** The presence of anti-HBs is generally interpreted as indicating recovery and immunity from hepatitis B virus infection. Anti-HBs also develops in a person who has been successfully vaccinated against hepatitis B.
- **Total hepatitis B core antibody (anti-HBc):** Appears at the onset of symptoms in acute hepatitis B and persists for life. The presence of anti-HBc indicates previous or ongoing infection with hepatitis B virus in an undefined time frame.
- **IgM antibody to hepatitis B core antigen (IgM anti-HBc):** Positivity indicates recent infection with hepatitis B virus ( $\leq 6$  mos). Its presence indicates acute infection.

## Appendix 8. Contraception Requirements for MEDI4736

- Females of childbearing potential who are sexually active with a nonsterilized male partner must use at least 1 highly effective method of contraception from screening, and must agree to continue using such precautions for 90 days after the last dose of MEDI4736 monotherapy; cessation of birth control after this point should be discussed with a responsible physician. Female subjects must use a hormonal method (eg, “the pill”) in addition to a barrier method (ie, male condom plus spermicide), to ensure pregnancy does not occur. Not engaging in sexual activity is an acceptable practice; however, periodic abstinence, the rhythm method, and the withdrawal method are not acceptable methods of birth control. Female subjects should refrain from breastfeeding and egg cell donation throughout this period.
- It is strongly recommended for the male partner of a female subject to also use a male condom plus spermicide throughout this period.
  - Females of childbearing potential are defined as those who are not surgically sterile (ie, bilateral tubal ligation, bilateral oophorectomy, or complete hysterectomy) or postmenopausal (defined as 12 months with no menses without an alternative medical cause)
  - The acceptable methods of contraception are described in [Table 4](#). A highly effective method of contraception is defined as 1 that results in a low failure rate (ie, less than 1% per year) when used consistently and correctly. Not all methods of acceptable contraception are highly effective.
- Nonsterilized male subjects who are sexually active with a female partner of childbearing potential must use a male condom plus spermicide from Day 1 and for 90 days after the last dose of MEDI4736 monotherapy. Not engaging in sexual activity is an acceptable practice; however, occasional abstinence, the rhythm method, and the withdrawal method are not acceptable methods of contraception. Male patients should refrain from sperm donation throughout this period.

It is strongly recommended for the female partner of a male subject to also use an effective method of contraception throughout this period.

- **All subjects:** Subjects should not donate blood while participating in this study and for 3 months following the last dose of study treatment.

**Table 4. Effective Methods of Contraception**

Barrier/Intrauterine Method	Hormonal Methods
Male or female condom with or without spermicide a,b,c	Implants
Cap, diaphragm, or sponge with spermicide a,b,c	Hormone shot or injection
Copper T intrauterine device	Combined pill
Levonorgesterel-releasing intrauterine system (eg, Mirena®) d	Minipillb
	Patch

- a. Female partners of male subjects must use an effective method of birth control.
- b. Only highly effective (<1% pregnancy rate per year) when used with additional methods of birth control.
- c. A combination of male condom with either cap, diaphragm, or sponge with spermicide (double-barrier methods) are also considered acceptable, but not highly effective, birth control methods.
- d. This is also considered a hormonal method.

## Appendix 9. Child-Pugh Score for Subjects with Liver Impairment

Measure	1 point	2 points	3 points
Total bilirubin, $\mu$ mol/L (mg/dL)	<34 (<2)	34-50 (2-3)	>50 (>3)
Serum albumin, g/L (g/dL)	>35 (>3.5)	28-35 (2.8-3.5)	<28 (<2.8)
PT/INR	<1.7	1.71-2.30	>2.30
Ascites	None	Mild	Moderate to Severe
Hepatic encephalopathy	None	Grade I-II (or suppressed with medication)	Grade III-IV (or refractory)

Points	Class
5-6	A
7-9	B
10-15	C

Source:

MRI	magnetic resonance imaging
MTD	Maximum tolerated dose
NCI	National Cancer Institute
NE	not evaluable
ORR	overall response rate
OS	overall survival
PCYC	Pharmacyclics LLC
PD	progressive disease
PFS	Progression free survival

Abbreviation	Definition
PK	Pharmacokinetic
PLT	platelets
PR	partial response
RP2D	Recommended Phase 2 dose
SAP	statistical analysis plan
SD	stable disease
SOC	system organ class
TEAE	Treatment-emergent adverse events
TNM	Tumor node metastases staging
TTP	time to progression
TTR	time to response
UNK	unknown
WBC	white blood count
WHO	World Health Organization

1. INTRODUCTION

This statistical analysis plan (SAP) lays out key elements including definitions and statistical methods for analysis of data in evaluation of efficacy and safety for the PCYC-1135-CA study. Analyses of pharmacokinetics data and biomarkers will be addressed in separate documents.

1.1. Study Design

This is a non-randomized, open-label, multi-center, Phase 1b/2 study to evaluate the efficacy and safety of ibrutinib in combination with durvalumab in subjects with relapsed or refractory solid tumor types (Stage III/IV per TNM staging):

- Non-small Cell Lung cancer (NSCLC): adenocarcinoma or squamous-cell carcinoma
- Breast cancer: HER2 positive or triple negative
- Pancreatic cancer: adenocarcinoma

RECIST 1.1 criteria will be used to evaluate response and document objective disease progression.

Phase 1b:

Phase 1b will follow a 6+3 dose de-escalation design to evaluate dose limiting toxicity (DLT) and determine the recommended phase 2 dose (RP2D) or maximum tolerated dose (MTD) for this study. In cohort 1 (consisting of 6 subjects regardless of tumor type), ibrutinib will be administered PO at a dose of 560 mg daily in combination with durvalumab at a dose of 10 mg/kg IV every 2 weeks in 28-day cycles until DLT or disease progression occurs. The DLT observation period includes Cycle 1 and laboratory assessments on Day 1 of Cycle 2 which will occur before the durvalumab infusion on Day 1 of Cycle 2. If 2 subjects within the initial cohort of 6 subjects experience a DLT, an additional 3 subjects will be enrolled at the same dose level. If 3 or more of 6 subjects experience a DLT, dose de-escalation will occur. If the subject incidence of DLTs during the first 28 days (Cycle 1=28 days and including laboratory assessments on Day 1 Cycle 2) of study treatment is <33.3% (ie, ≤ 1 of 6 or ≤ 2 of 9), this dose level will be considered safe to proceed to Phase 2, and will be defined as the RP2D. A DLT is defined as any Grade 3 or higher non-hematologic or Grade 4 hematologic AE possibly related to study treatment(s) occurring during the DLT observation period.

A similar 6+3 cohort design will be utilized in the dose de-escalation cohorts (see Table 1). De-escalation cohorts -1A and -1B will be opened simultaneously to determine which dosing schedule is most appropriate for the phase 2 portion of the study. Determination of the RP2D will be based on the safety profile of the 2 treatment regimens. If necessary, the dose de-escalation cohort -2 will be enrolled thereafter.

Table 1: Phase 1b Dosing Levels

28-Day Dosing Cycle	Ibrutinib	MEDI4736
Cohort 1	560 mg once daily PO	10 mg/kg IV
Cohort -1A*	420 mg once daily PO	10 mg/kg IV
Cohort -1B*	560 mg once daily PO	3 mg/kg IV
Cohort -2	420 mg once daily PO	3 mg/kg IV

*: Cohorts -1A and -1B are 2 parallel cohorts and will be enrolled concurrently in the sequence of -1A followed by -1B.

After the RP2D is determined, enrollment in Phase 2 will commence. Subjects who were not treated at the RP2D in Phase 1b will continue to be treated at the assigned dose. All subjects enrolled under Phase 1b will be followed for response evaluation and overall survival.

Phase 2:

Subjects with one of three solid tumor types (Stage III/IV) will be enrolled per the specifications below.

- NSCLC (adenocarcinoma and squamous-cell carcinoma at an approximate 2:1 ratio) (ie, at least 15 subjects with squamous-cell carcinoma will be enrolled)
- Breast cancer (triple-negative and HER2-positive cancer at an approximate 2:1 ratio) (ie, 15 subjects with triple-negative breast cancer will be enrolled)
- Pancreatic Cancer Cohort: (adenocarcinoma)

For each of the above three cohorts, the statistical framework of Simon's optimal 2-stage design will be implemented to enroll subjects (an interim analysis for futility in the first stage and the final analysis in the second stage). The interim analysis for futility will be performed to evaluate the response and safety profile. Enrollment will continue while the interim analysis is performed. A cohort may be discontinued based on the interim efficacy and/or safety results. The decisions based on the results of the interim analysis are independent in the 3 individual disease cohorts. At the time of the interim safety assessment, Investigators that enrolled subjects and the Sponsor (at a minimum: a Medical Monitor, a Drug Safety representative, and a Biostatistician) will review safety data and make recommendations for the conduct of the study: continue the trial unchanged, consider modifying in part or in whole, or stop the trial due to safety concerns.

NSCLC and breast cancer cohorts (n=43 per cohort):

The breast and NSCLC cohorts will each enroll 43 evaluable subjects. Subjects who discontinue prior to the first tumor response assessment for reasons other than progressive disease will not be considered evaluable for response. An interim analysis for futility will be performed for each cohort independently after first 18 subjects in a cohort are evaluable for tumor response. If 2 or fewer responders are observed among the 18 evaluable subjects, the Sponsor may consider discontinuation of this cohort; however, assessment of biomarkers (that may aid in prospective

enrichment for responders) or tumor measurements (showing clinically relevant tumor reductions, ie, <30%, that fit the criteria for SD) may support continued enrollment.

Pancreatic cancer cohort (n=44):

This cohort will enroll 44 evaluable subjects. An interim analysis for futility will be performed after 17 subjects are evaluable for tumor response. If 1 or no responder is observed among the first 17 evaluable subjects, the Sponsor may consider discontinuation of this cohort. Same as in the other two cohorts, the assessment of biomarkers or tumor measurements may support continued enrollment.

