1.4. Sample Size Determination

The study is not powered for comparison of dose cohorts or tumor type cohorts.

Phase 1b: Dose de-escalation will follow the 6+3 design and up to four dose cohorts will be enrolled for the DLT to determine the RP2D for the combination therapy. Therefore, Phase 1b will enroll a minimum of 6 and a maximum of 36 evaluable subjects.

Phase 2: Hypothesis for the true response rate will be tested as described below independently for each tumor type cohort based on the statistical framework of Simon's optimal 2-stage design. With a 1-sided error rate of 0.05, each tumor type cohort would have 80% power based on the true response rate in the alternative hypothesis. Approximately 130 subjects (including the subjects treated at the RP2D in Phase 1b and with the tumor type) across the three tumor type cohorts will be included in the Phase 2 analyses.

NSCLC cohort and breast cancer cohort (n=18 for interim and n=43 for final per cohort):

For each of the two tumor type cohorts, a true response rate of 10% (H_0) versus 25% (H_a) will be tested and the probability of early stopping is at least 73.4% if the true response rate is $\leq 10\%$ (H_0), and no greater than 13.5% if the true response rate is $\geq 25\%$ (H_a).

An interim analysis (for futility) will be performed based on the first 18 evaluable subjects for each cohort independently. If 2 or fewer responders are observed among the 18 evaluable subjects in a cohort, the enrollment may be stopped. Otherwise, the cohort will continue to enroll an additional 25 evaluable subjects for a total of 43 evaluable subjects for the final analysis. The null hypothesis will be rejected if 8 or more responders are observed among the 43 evaluable subjects.

Each cohort will enroll subjects according to the histology ratio described in Section 1.1.

Pancreatic cancer cohort (n=17 for interim and n=44 for final):

A true response rate of 5% (H_0) versus 18% (H_a) will be tested and the probability of early stopping is at least 79.2% if the true response rate is $\leq 5\%$ (H_0), and no greater than 16.2% if the true response rate is $\geq 18\%$ (H_a).

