An interim analysis (for futility) will be performed based on the first 17 evaluable subjects. If 1 or no responder is observed among the 17 evaluable subjects, the enrollment may be stopped. Otherwise, this cohort will continue to enroll an additional 27 evaluable subjects for a total of 44 evaluable subjects for the final analysis. The null hypothesis will be rejected if 5 or more responders are observed among the 44 evaluable subjects.

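### The 1-sided 0.05 per cohort is not guaranteed: the futility stops are optional while 8/43 and 5/44 stay fixed, so size can reach 6.1% (NSCLC, breast) or 6.7% (pancreas)

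*SAP*

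**What the plan says.** SAP 1.4 makes the error claim: "With a 1-sided error rate of 0.05, each tumor type cohort would have 80% power". The Protocol synopsis (Sample Size Determination) and Protocol 10.4.2 make the same claim.

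Every statement of the stop is permissive.

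- **NSCLC and breast.** SAP 1.1 says that with 2 or fewer responders "the Sponsor may consider discontinuation of this cohort; however, assessment of biomarkers" or "tumor measurements (showing clinically relevant tumor reductions, ie, <30%, that fit the criteria for SD) may support continued enrollment". SAP 1.4 says: "If 2 or fewer responders are observed among the 18 evaluable subjects in a cohort, the enrollment may be stopped".
- **Pancreas.** SAP 1.1 says: "If 1 or no responder is observed among the first 17 evaluable subjects, the Sponsor may consider discontinuation of this cohort". It then allows the same grounds for continuing as in the other cohorts. SAP 1.4 says: "If 1 or no responder is observed among the 17 evaluable subjects, the enrollment may be stopped".
- **Protocol.** The synopsis, 3.1 and 10.4.2 use the same kind of wording.

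The final rules do not depend on what happened at the interim. For NSCLC and breast, with 43 evaluable subjects: "The null hypothesis will be rejected if 8 or more responders are observed". For pancreas, with 44: "The null hypothesis will be rejected if 5 or more responders are observed". Neither document gives another cut-off, bars rejection for a cohort that continued after meeting the boundary, or calls the boundary non-binding. The list of changes in SAP 5 does not mention the matter.

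The two looks count responses differently. Protocol 10.6.2 and SAP 1.5.2 do not require confirmation at the interim. Protocol 10.6.2 requires it for the primary analysis, and SAP Table 2 defines ORR with confirmation.

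**The concern.** A Simon design spends its type I error on the understanding that a cohort at or below the stage 1 boundary stops and cannot reject. If such a cohort may run on to 43 or 44 subjects and reject at the same count, the probability of a false rejection rises. This branch is not remote: by the plan's own figures, 73.4% (NSCLC, breast) and 79.2% (pancreas) of cohorts with no useful activity meet the boundary. A cohort with 2/18 that ends at 8/43 would be reported as rejecting the null hypothesis at 0.05, although the plan does not guarantee that level.

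**Working it through.** **Inputs** (SAP 1.3 and 1.4, Protocol 10.4.2). NSCLC and breast: p0 = 10%, p1 = 25%, stage 1 boundary 2/18, reject at 8/43. Pancreas: p0 = 5%, p1 = 18%, boundary 1/17, reject at 5/44. Write r1 for the boundary, n1 for the stage 1 size, r for the final cut-off and n for the total. Results are given as NSCLC and breast / pancreas.

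**1. The plan's own figures, stops obeyed, one response definition.**
Rejection probability = sum over x > r1 of P(Bin(n1, p) = x) × P(Bin(n − n1, p) ≥ r − x).

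- Early stopping under H0: 73.4% / 79.2%. Under Ha: 13.5% / 16.2%. All four match the documents.
- Size: 0.0480 / 0.0469. Power: 0.8003 / 0.8037. The stated 0.05 and 80% are therefore the figures for obeyed stops.

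**2. What the failed cohorts add if continued with the cut-off unchanged.**
The added term is the same sum over x ≤ r1, at p0.

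- NSCLC, breast: 0.1501 × 0.00226 + 0.3002 × 0.00948 + 0.2835 × 0.03340 = 0.0127.
- Pancreas: 0.4181 × 0.01002 + 0.3741 × 0.04374 = 0.0206.

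Total size if all failed cohorts continue:

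- P(Bin(43, 0.10) ≥ 8) = 0.0607.
- P(Bin(44, 0.05) ≥ 5) = 0.0675 (0.06748, so 6.7%).

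This is the maximum under any interim rule. Rejection requires the final confirmed count to reach 8 or 5, and stopping can only remove cases from that event.

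**3. Partial override, one definition, stage 1 count fixed.**
If a share f of failed null cohorts continues regardless of the count, size = obeyed size + f × added term.

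| f | NSCLC, breast | Pancreas |
|---|---|---|
| 0 | 4.8% | 4.7% |
| 25% | 5.1% | 5.2% |
| 50% | 5.4% | 5.7% |
| 100% | 6.1% | 6.7% |

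Size passes 5% at f = (0.05 − obeyed size) / added term, which is about 16% / 15%. Late responders raise this share. If 90% / 80% / 70% of eventual stage 1 responders are visible at the interim (an assumption; the documents give no figure), it becomes 41% / 56% / 66% for NSCLC and breast, and 32% / 44% / 52% for pancreas.

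**4. The interim definition the plan actually uses.**
Let a share c of responses be confirmed, and hold the confirmed rate at p0. Stage 1 unconfirmed responders are then U ~ Bin(n1, p0/c), and confirmed responders given U are Bin(U, c). The boundary applies to U and the final cut-off to confirmed responses. The documents give no value for c, so the table shows an assumed range.

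| c | Obeyed size, NSCLC and breast | Obeyed size, pancreas |
|---|---|---|
| 90% | 4.98% | 4.84% |
| 80% | 5.17% | 5.01% |
| 70% | 5.37% | 5.22% |

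The reason is that unconfirmed responses let more null cohorts past the interim. At c = 80%, the chance of meeting the boundary under H0 falls from 73.4% / 79.2% to 60.5% / 71.2%.

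**The case against.** The case for leaving the plan alone is reasonable. A non-binding futility look is a legitimate choice in a single-arm, open-label study that the Protocol itself calls exploratory, and the permissive wording is disclosed consistently in both documents. The maximum needs every failed cohort to continue. The stated grounds for continuing also fit the calculation poorly. Biomarker enrichment may change the null rate, so that 10% and 5% no longer apply. Shrinkage short of a partial response points to late responders, and those raise the share of overrides needed to pass 5%.

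Most of this stands, and it is why the point is minor. It does not rescue the stated figure, because a non-binding boundary needs its type I error quoted without credit for the stop.

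Two stronger readings are tempting, and the documents support neither.

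- A reader might infer that size exceeds 5% in any case. The documents do not say how often failed cohorts would be continued, and with one response definition and few overrides size stays below 5%.
- A reader might infer that obeying the stops, or raising the cut-off for continued cohorts, would secure 5%. The difference between unconfirmed responses at the interim and confirmed responses at the end means that neither is assured.

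**Conclusion.** The concern holds as a minor point. The plan states a 1-sided 0.05 per cohort that it does not guarantee. The maximum is 6.1% for NSCLC and breast and 6.7% for pancreas, an excess over 5% of at most 1.1 and 1.7 points.

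The maxima assume 43 and 44 evaluable subjects with confirmed response rates of 10% and 5% in both stages. They do not depend on the interim response definition or on late responders. They do not apply if stage 2 is biomarker-enriched so that the null rate changes. The 4.8% / 4.7% and the 16% / 15% crossing need more: one response definition at both looks and a stage 1 count that does not change after the interim. The plan does not meet the first of these, and the second may not hold, since the interim needs only one assessment and Protocol 7.2.3.1 warns of delayed responses.

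**What to change.** In the Protocol synopsis (Sample Size Determination), Protocol 10.4.2 and SAP 1.4, state that the futility boundary is non-binding and that the 1-sided type I error with 8/43 and 5/44 is up to 6.1% (NSCLC, breast) and 6.7% (pancreas). This costs no power and keeps the freedom to continue. The price is a slightly less favourable stated figure and, for the Protocol text, the amendment approvals required by Protocol 12.14.

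If the sponsor prefers a higher cut-off for cohorts continued after meeting the boundary, 10/43 and 7/44 give 4.9% / 4.8%, but only with one response definition at both looks. With 90% / 80% / 70% of responses confirmed, they give 5.04% / 5.22% / 5.41% (NSCLC, breast) and 4.92% / 5.08% / 5.28% (pancreas). The cut-offs would therefore have to be recomputed for the interim definition actually used. Barring rejection in such cohorts gives the obeyed sizes in step 4 and carries the same caveat.

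Separately, SAP 1.6 sets a 2-sided 0.05 for the final ORR analysis, against the 1-sided 0.05 in SAP 1.4. Reconcile them by stating that the responder-count rule decides.
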